## 10.3 Attribution to agent(s) or procedure

When assessing whether an adverse event (AE) is related to a medical agent(s) medical or procedure, the following attribution categories are utilized:

Definite - The AE *is clearly related* to the agent(s)/procedure.

Probable - The AE *is likely related* to the agent(s)/procedure.

Possible - The AE *may be related* to the agent(s)/procedure.

Unlikely - The AE *is doubtfully related* to the agent(s)/procedure.

Unrelated - The AE *is clearly NOT related* to the agent(s)/procedure.

### 10.31 EXPECTED Serious Adverse Events: Protocol Specific Exceptions to Expedited Reporting

For this protocol only, the following Adverse Events/Grades are expected to occur within this population and do not require Expedited Reporting. These events must still be reported via Routine Reporting (see Section 10.6).\*

\*Report any clinically important increase in the rate of a serious suspected adverse reaction (at your study site) over that which is listed in the protocol or investigator brochure as an expedited event.

\*Report an expected event that is greater in severity or specificity than expected as an expedited event.

CTCAE System/Organ/Class (SOC)	Adverse event/ Symptoms	CTCAE Grade at which the event will not be reported in an expedited manner 
Blood and lymphatic system disorders	Anemia	≤Grade 3
	Febrile neutropenia	≤Grade 3
Cardiac Disorders	Myocardial infarction	≤Grade 3

CTCAE System/Organ/Class (SOC)	Adverse event/ Symptoms	CTCAE Grade at which the event will not be reported in an expedited manner 
Endocrine disorders	Hypothyroidism	≤Grade 3
	Hyperthyroidism	≤Grade 3
	Hypophysitis	≤Grade 3
Gastrointestinal disorders	Abdominal pain	≤Grade 3
	Diarrhea	≤Grade 3
	Gastric hemorrhage	≤Grade 3
	Nausea	≤Grade 3
	Vomiting	≤Grade 3
General disorders and administrations site conditions	Fatigue	≤Grade 3
	Fever	≤Grade 3
Immune system disorders	Allergic reaction	≤Grade 3
	Anaphylaxis	≤Grade 3
Infections and infestations	Hepatitis viral	≤Grade 3
Injury, poisoning, and procedural complications	Wound dehiscence	≤Grade 3
Investigations	Alkaline phosphatase increased	≤Grade 3
	Aspartate aminotransferase increased	≤Grade 3
	Blood bilirubin increased	≤Grade 3
	Neutrophil count decreased	≤Grade 4
	Platelet count decreased	≤Grade 3
	White blood cell decreased	≤Grade 4
Musculoskeletal and connective tissue disorders	Arthralgia	≤Grade 3
	Myalgia	≤Grade 3
Respiratory, thoracic and mediastinal disorders	Pneumonitis	≤Grade 3
Nervous system disorders	Intracranial hemorrhage	≤Grade 3
	Leukoencephalopathy	≤Grade 3
	Peripheral sensory neuropathy	≤Grade 3
Renal and urinary disorders	Proteinuria	≤Grade 4
Respiratory, thoracic and mediastinal disorders	Bronchopulmonary hemorrhage	≤Grade 3
Skin and subcutaneous tissue disorders	Rash acneiform	≤Grade 4
	Rash maculo-papular	≤Grade 4
Vascular disorders	Hypertension	≤Grade 3
	Thromboembolic event	≤Grade 3

 These exceptions only apply if the adverse event does not result in hospitalization. If the adverse event results in hospitalization, then the standard expedited adverse events reporting requirements must be followed.

Specific protocol exceptions to expedited reporting should be reported expeditiously by investigators **ONLY** if they exceed the expected grade of the event.

The following hospitalizations are not considered to be SAEs because there is no “adverse event” (*i.e.*, there is no untoward medical occurrence) associated with the hospitalization:

- Hospitalizations for respite care
- Planned hospitalizations required by the protocol
- Hospitalization planned before informed consent (where the condition requiring the hospitalization has not changed post study drug administration)
- Hospitalization for elective procedures unrelated to the current disease and/or treatment on this trial
- Hospitalization for administration of study drug or insertion of access for administration of study drug
- Hospitalization for routine maintenance of a device (*e.g.*, battery replacement) that was in place before study entry
- Hospitalization, or other serious outcomes for signs and symptoms of progression of the cancer.

#### 10.4 Expedited Reporting Requirements for IND/IDE Agents

##### 10.41 Phase 1 and Early Phase 2 Studies: Expedited Reporting Requirements for Adverse Events that Occur on Studies under an IND/IDE within 30 Days of the Last Administration of the Investigational Agent/Intervention

FDA REPORTING REQUIREMENTS FOR SERIOUS ADVERSE EVENTS (21 CFR Part 312)		

NOTE: Investigators MUST immediately report to the sponsor ANY Serious Adverse Events, whether or not they are considered related to the investigational agent(s)/intervention (21 CFR 312.64)
 
An adverse event is considered serious if it results in ANY of the following outcomes:
 
 
○ Death
 
○ A life-threatening adverse event
 
○ An adverse event that results in inpatient hospitalization or prolongation of existing hospitalization for ≥24 hours
 
○ A persistent or significant incapacity or substantial disruption of the ability to conduct normal life functions
 
○ A congenital anomaly/birth defect.
 
○ Important Medical Events (IME) that may not result in death, be life threatening, or require hospitalization may be considered serious when, based upon medical judgment, they may jeopardize the patient or subject and may require medical or surgical intervention to prevent one of the outcomes listed in this definition. (FDA, 21 CFR 312.32; ICH E2A and ICH E6).
 
		

ALL SERIOUS adverse events that meet the above criteria MUST be immediately reported to the sponsor within the timeframes detailed in the table below.
		
Hospitalization	Grade 1 and Grade 2 Timeframes	Grade 3-5 Timeframes
Resulting in Hospitalization ≥24 hrs	7 Calendar Days	24-Hour 3 Calendar Days
Not resulting in Hospitalization ≥24 hrs	Not required	

**Expedited AE reporting timelines are defined as:**

- “24-Hour; 3 Calendar Days” - The AE must initially be reported within 24 hours of learning of the AE, followed by a complete expedited report within 3 calendar days of the initial 24-hour report.
- “7 Calendar Days” - A complete expedited report on the AE must be submitted within 7 calendar days of learning of the AE.

Serious adverse events that occur more than 30 days after the last administration of investigational agent/intervention and have an attribution of possible, probable, or definite require reporting as follows:

**Expedited 24-hour notification followed by complete report within 3 calendar days for:**

- All Grade 4, and Grade 5 AEs

**Expedited 7 calendar day reports for:**

- Grade 2 adverse events resulting in hospitalization or prolongation of hospitalization
- Grade 3 adverse events

 For studies using PET or SPECT IND agents, the AE reporting period is limited to 10 radioactive half-lives, rounded UP to the nearest whole day, after the agent/intervention was last administered. Footnote “1” above applies after this reporting period.

Effective Date: May 5, 2011 Effective Date: May 5, 2011

NOTE: Refer to Section 10.32 for exceptions to Expedited Reporting

#### 10.42 General reporting instructions

The Mayo IND Coordinator will assist the sponsor-investigator in the processing of expedited adverse events and forwarding of suspected unexpected serious adverse reactions (SUSARs) to the FDA and IRB.

**Mayo Clinic Sites:** Use Mayo Expedited Event Report form

[REDACTED] or investigational agents or commercial/investigational agents on the same arm.

For commercial agents:

[REDACTED]

And send a copy to Genentech Drug Safety:

[REDACTED]

**Non-MCCC Institutions:**

[REDACTED]

And send a copy to Genentech Drug Safety:

[REDACTED]

#### 10.43 Reporting of re-occurring SAEs

ALL SERIOUS adverse events that meet the criteria outlined in table 10.41 MUST be immediately reported to the sponsor within the timeframes detailed in the corresponding table. This reporting includes, but is not limited to SAEs that re-occur again after resolution.

## 10.5 Other Required Reporting

### 10.51 Unanticipated Problems Involving Risks to Subjects or Others (UPIRTSOS)

Unanticipated Problems Involving Risks to Subjects or Others (UPIRTSOS) in general, include any incident, experience, or outcome that meets **all** of the following criteria:

- Unexpected (in terms of nature, severity, or frequency) given (a) the research procedures that are described in the protocol-related documents, such as the IRB-approved research protocol and informed consent document; and (b) the characteristics of the subject population being studied;
- Related or possibly related to participation in the research (in this guidance document, possibly related means there is a reasonable possibility that the incident, experience, or outcome may have been caused by the procedures involved in the research); and
- Suggests that the research places subjects or others at a greater risk of harm (including physical, psychological, economic, or social harm) than was previously known or recognized.

Some unanticipated problems involve social or economic harm instead of the physical or psychological harm associated with adverse events. In other cases, unanticipated problems place subjects or others at increased *risk* of harm, but no harm occurs.

Note: If there is no language in the protocol indicating that pregnancy is not considered an adverse experience for this trial, and if the consent form does not indicate that subjects should not get pregnant/impregnate others, then any pregnancy in a subject/patient or a male patient's partner (spontaneously reported) which occurs during the study or within 120 days of completing the study should be reported as a UPIRTSO.

#### **Mayo Clinic Cancer Center (MCCC) Institutions:**

If the event meets the criteria for IRB submission as a Reportable Event/UPIRTSO, provide the Reportable Event coversheet and appropriate documentation to [REDACTED] The Mayo Regulatory Affairs Office will review and process the submission to the Mayo Clinic IRB.

### 10.52 Death

**Note: A death on study requires both routine and expedited reporting regardless of causality, unless as noted below. Attribution to treatment or other cause must be provided.**

Any death occurring within 30 days of the last dose, regardless of attribution to an agent/intervention under an IND/IDE requires expedited reporting within 24-hours.

Any death occurring greater than 30 days with an attribution of possible, probable, or definite to an agent/intervention under an IND/IDE requires expedited reporting within 24-hours.

#### **Reportable categories of Death**

- Death attributable to a CTCAE term.
- Death Neonatal: A disorder characterized by cessation of life during the first 28 days of life.

- Death NOS: A cessation of life that cannot be attributed to a CTCAE term associated with Grade 5.
- Sudden death NOS: A sudden (defined as instant or within one hour of the onset of symptoms) or an unobserved cessation of life that cannot be attributed to a CTCAE term associated with Grade 5.
- Death due to progressive disease should be reported as Grade 5 “Neoplasms benign, malignant and unspecified (including cysts and polyps) – Other (Progressive Disease)” under the system organ class (SOC) of the same name. Evidence that the death was a manifestation of underlying disease (e.g., radiological changes suggesting tumor growth or progression: clinical deterioration associated with a disease process) should be submitted.

#### 10.53 Secondary Malignancy

- A **secondary malignancy** is a cancer caused by treatment for a previous malignancy (e.g., treatment with investigational agent/intervention, radiation or chemotherapy). A secondary malignancy is not considered a metastasis of the initial neoplasm.
- All secondary malignancies that occur following treatment with an agent under an IND/IDE will be reported. Three options are available to describe the event:
  - Leukemia secondary to oncology chemotherapy (e.g., Acute Myelocytic Leukemia [AML])
  - Myelodysplastic syndrome (MDS)
  - Treatment-related secondary malignancy
- Any malignancy possibly related to cancer treatment (including AML/MDS) should also be reported via the routine reporting mechanisms outlined in each protocol.

#### 10.54 Second Malignancy

A second malignancy is one unrelated to the treatment of a prior malignancy (and is NOT a metastasis from the initial malignancy). Second malignancies require ONLY routine reporting unless otherwise specified-

#### 10.55 Pregnancy, Fetal Death, and Death Neonatal

If a female subject (or female partner of a male subject) taking investigational product becomes pregnant, the subject taking should notify the Investigator, and the pregnant female should be advised to call her healthcare provider immediately. The patient should have appropriate follow-up as deemed necessary by her physician. If the baby is born with a birth defect or anomaly, a second expedited report is required.

Prior to obtaining private information about a pregnant woman and her infant, the investigator must obtain consent from the pregnant woman and the newborn infant's parent or legal guardian before any data collection can occur. A consent form will need to be submitted to the IRB for these subjects if a pregnancy occurs. If informed consent is not obtained, no information may be collected.

In cases of fetal death, miscarriage or abortion, the mother is the patient. In cases where the child/fetus experiences a serious adverse event other than fetal death, the child/fetus is the patient.

NOTE: When submitting Mayo Expedited Adverse Event Report reports for “Pregnancy”, “Pregnancy loss”, or “Neonatal loss”, the potential risk of exposure of the fetus to the investigational agent(s) or chemotherapy agent(s) should be

documented in the “Description of Event” section. Include any available medical documentation. Include this form:

10.551 Pregnancy

Pregnancy should be reported in an expedited manner as **Grade 3 “Pregnancy, puerperium and perinatal conditions - Other (pregnancy)”** under the Pregnancy, puerperium and perinatal conditions SOC. Pregnancy should be followed until the outcome is known.

10.552 Fetal Death

Fetal death is defined in CTCAE as “A disorder characterized by death in utero; failure of the product of conception to show evidence of respiration, heartbeat, or definite movement of a voluntary muscle after expulsion from the uterus, without possibility of resuscitation.”

Any fetal death should be reported expeditiously, as **Grade 4 “Pregnancy, puerperium and perinatal conditions - Other (pregnancy loss)”** under the Pregnancy, puerperium and perinatal conditions SOC.

10.553 Death Neonatal

Neonatal death, defined in CTCAE as “A disorder characterized by cessation of life occurring during the first 28 days of life” that is felt by the investigator to be at least possibly due to the investigational agent/intervention, should be reported expeditiously.

A neonatal death should be reported expeditiously as **Grade 4 “General disorders and administration - Other (neonatal loss)”** under the General disorders and administration SOC.

10.56 AEs of Special Interest (AESIs)

AEs of Special Interest are defined as a potential safety problem, identified as a result of safety monitoring of the Product. AESIs are a subset of Events to Monitor (EtMs) of scientific and medical concern specific to the product, for which ongoing monitoring and rapid communication by the Investigator to the Sponsor is required. Such an event might require further investigation in order to characterize and understand it. Depending on the nature of the event, rapid communication by the trial Sponsor to other parties (e.g., Regulatory Authorities) may also be warranted.

Adverse events of special interest for this study include the following:

- Cases of potential drug-induced liver injury that include an elevated ALT or AST in combination with either an elevated bilirubin or clinical jaundice, as defined by Hy’s law:
  - Treatment-emergent ALT or AST  $>3 \times$  ULN in combination with total bilirubin  $>2 \times$  ULN
  - Treatment-emergent ALT or AST  $>3 \times$  ULN in combination with clinical jaundice
- Data related to a suspected transmission of an infectious agent by the study drug (STIAMP), as defined below:

Any organism, virus, or infectious particle (e.g., prion protein transmitting transmissible spongiform encephalopathy), pathogenic or non-pathogenic, is considered an infectious agent. A transmission of an infectious agent may be suspected from clinical symptoms or laboratory findings that indicate an infection in a patient exposed to a medicinal product. This term applies only when a contamination of the study drug is suspected

**10.561 Adverse Events of Special Interest specific to Atezolizumab and/or Tiragolumab:**

- Pneumonitis
- Colitis
- Endocrinopathies: diabetes mellitus, pancreatitis, adrenal insufficiency, hyperthyroidism, and hypophysitis
- Hepatitis, including AST or ALT > 10 × ULN
- Systemic lupus erythematosus
- Neurological disorders: Guillain-Barré syndrome, myasthenic syndrome or myasthenia gravis, and meningoencephalitis
- Events suggestive of hypersensitivity, infusion-related reactions, cytokine release syndrome, macrophage activating syndrome, and hemophagocytic lymphohistiocytosis
- Nephritis
- Ocular toxicities (e.g., uveitis, retinitis, optic neuritis)
- Myositis
- Myopathies, including rhabdomyolysis
- Grade ≥2 cardiac disorders (e.g., atrial fibrillation, myocarditis, pericarditis)
- Vasculitis
- Autoimmune hemolytic anemia
- Severe cutaneous reactions (e.g. Stevens-Johnson Syndrome, dermatitis bullous, toxic epidermal necrolysis)
- Myelitis
- Facial paresis

**10.562 Adverse events of Special Interest Specific to Vemurafenib:**

- Acute kidney injury
- Cutaneous squamous cell carcinomas
- Liver injury
- Non cutaneous squamous cell carcinomas
- Pancreatitis
- Progression of RAS mutant malignancies
- QT prolongation

**10.563 Adverse events of Special Interest Specific to Cobimetinib:**

- Any grade serous retinopathy, including events of retinal detachment, retinal pigment epithelium detachment, neurosensory retinal detachment or central serous chorioretinopathy
- Significant liver toxicity: AST and/or ALT > 10 X upper limit of normal

- Symptomatic heart failure / Grade  $\geq 2$  left ventricular dysfunction
- Grade  $\geq 3$  CPK elevation or rhabdomyolysis
- Grade  $\geq 3$  diarrhea
- Grade  $\geq 3$  rash

## 10.6 Required Routine Reporting

### 10.61 Baseline and Adverse Events Evaluations

Pretreatment symptoms/conditions to be graded at baseline and adverse events to be graded at each evaluation.

Grading is per CTCAE v4.0 **unless** alternate grading is indicated in the table below:

CTCAE System Organ Class (SOC)	Adverse event/Symptoms	Baseline	Each evaluation
Blood and lymphatic system disorders	Anemia	X	X
Gastrointestinal disorders	Baseline # stools	X	
	Diarrhea		X
General disorders	Fatigue	X	X
	Fever		X
Immune system disorders	Allergic reaction		X
	Anaphylaxis		X
Investigations	Blood bilirubin increased	X	X
Respiratory, thoracic and mediastinal disorders	Dyspnea	X	X
Skin and subcutaneous tissue disorders	Rash, acneiform	X	X
	Rash, maculo-papular	X	X

### 10.62 Other routine reporting

Submit via appropriate MCCC Case Report Forms (i.e., paper or electronic, as applicable) the following AEs experienced by a patient and not specified in Section 10.6:

- 10.621 Grade 2 AEs deemed *possibly, probably, or definitely* related to the study treatment or procedure.
- 10.622 Grade 3 and 4 AEs regardless of attribution to the study treatment or procedure.
- 10.623 Grade 5 AEs (Deaths)
- 10.6231 Any death within 30 days of the patient's last study treatment or procedure regardless of attribution to the study treatment or procedure.
- 10.6232 Any death more than 30 days after the patient's last study treatment or procedure that is felt to be at least possibly treatment related must also be submitted as a Grade 5 AE, with a CTCAE type and attribution assigned.

## 10.7 Late Occurring Adverse Events

Refer to the instructions in the Forms Packet (or electronic data entry screens, as applicable) regarding the submission of late occurring AEs following completion of the Active Monitoring Phase (i.e., compliance with Test Schedule in Section 4.0).

## 10.8 Genentech Additional Event Reporting Instructions

### **SAFETY REPORTING OF ADVERSE EVENTS**

#### 10.81 ASSESSMENT OF SAFETY

##### **Specification of Safety Variables**

Safety assessments will consist of monitoring and reporting adverse events (AEs) and serious adverse events

(SAEs) per protocol. This includes all events of death, and any study specific issue of concern.

##### **Adverse Events**

An AE is any unfavorable and unintended sign, symptom, or disease temporally associated with the use of an investigational medicinal product (IMP) or other protocol-imposed intervention, regardless of attribution.

This includes the following:

- ☐ AEs not previously observed in the subject that emerge during the protocol-specified AE reporting period, including signs or symptoms associated with [insert condition being studied] that were not present prior to the AE reporting period.
- ☐ Complications that occur as a result of protocol-mandated interventions (e.g., invasive procedures such as cardiac catheterizations)
- ☐ If applicable, AEs that occur prior to assignment of study treatment associated with medication washout, no treatment run-in, or other protocol-mandated intervention.
- ☐ Preexisting medical conditions (other than the condition being studied) judged by the investigator to have worsened in severity or frequency or changed in character during the protocol-specified AE reporting period.

##### **Serious Adverse Events**

An AE should be classified as an SAE if the following criteria are met:

- ☐ It results in death (i.e., the AE actually causes or leads to death).
- ☐ It is life threatening (i.e., the AE, in the view of the investigator, places the subject at immediate risk of death. It does not include an AE that, had it occurred in a more severe form, might have caused death.).
- ☐ It requires or prolongs inpatient hospitalization.
- ☐ It results in persistent or significant disability/incapacity (i.e., the AE results in substantial disruption of the subject's ability to conduct normal life functions).
- ☐ It results in a congenital anomaly/birth defect in a neonate/infant born to a mother exposed to the IMP.
- ☐ It is considered a significant medical event by the investigator based on medical judgment (e.g., may jeopardize the subject or may require medical/surgical intervention to prevent one of the outcomes listed above).

## 10.82 METHODS AND TIMING FOR ASSESSING AND RECORDING SAFETY VARIABLES

The investigator is responsible for ensuring that all AEs and SAEs that are observed or reported during the study, are collected and reported to the FDA, appropriate IRB(s), and Genentech, Inc. in accordance with CFR312.32 (IND Safety Reports).

### **Adverse Event Reporting Period**

The study period during which all AEs and SAEs must be reported begins after informed consent is obtained and initiation of study treatment and ends 30 days following the last administration of study treatment or study discontinuation/termination, whichever is earlier. After this period, investigators should only report SAEs that are attributed to prior study treatment.

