### 3.0 Patient Eligibility

#### 3.1 Pre-Registration – Inclusion Criteria

3.11 Age  $\geq 18$  years.

3.12 High-risk stage III melanoma, defined as (any of the following):

- recurrent nodal metastasis, or
- clinically detectable nodal metastasis, or
- metastatic involvement of more than one nodal basin

NOTE: For the purpose of pre-registration, high-risk stage III melanoma is defined based on clinical and imaging assessment (PET/CT, CT, or MRI). Histologic confirmation of nodal metastatic disease is not needed at the time of pre-registration, provided there is histologic confirmation of primary melanoma or a prior lymph node metastasis.

3.13 Willing to submit archival tissue from a lymph node biopsy or undergo a needle biopsy (with clip placement) for BRAF testing and for research purposes.

3.14 Willing to forego anticancer treatments or investigational agents during pre-registration period.

3.15 The following laboratory values obtained  $\leq 28$  days prior to pre-registration:

- Only for patients receiving therapeutic anticoagulation: stable anticoagulant regimen and stable INR

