### *Expedited Reporting*

Events reported to sponsor within 24 hours, 5 days or 10 days of study team becoming aware of the event.

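### The AE reporting period in Section 10.82 opens only once treatment starts, although Section 10.81 counts complications of pre-treatment study procedures such as the biopsy and clip as adverse events

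*Combined protocol and SAP*

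**What the plan says.** **Start of reporting.** Section 10.82 (Adverse Event Reporting Period) states that the period for AEs and SAEs "begins after informed consent is obtained and initiation of study treatment". The same sentence gives the end: the period "ends 30 days following the last administration of study treatment or study discontinuation/termination, whichever is earlier".

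**What counts as an adverse event.** Section 10.81 includes "Complications that occur as a result of protocol-mandated interventions (e.g., invasive procedures such as cardiac catheterizations"). It also includes, with the qualifier that this applies only where relevant, "AEs that occur prior to assignment of study treatment associated with medication washout, no treatment run-in, or other protocol-mandated intervention".

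**Procedures before treatment.** Criterion 3.13 requires the patient either to supply archival lymph node tissue or to "undergo a needle biopsy (with clip placement) for BRAF testing and for research purposes". The Arm C schedule in Section 4.2 has a pre-registration row for the biopsy (or an archival specimen) together with clip placement, marked as research funded.

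**Expedited timelines.** The definitions in Section 10.0 describe expedited reporting as "Events reported to sponsor within 24 hours, 5 days or 10 days of study team becoming aware of the event". Section 10.41 sets its own limits by grade and hospitalization. For one of its two categories it says: "A complete expedited report on the AE must be submitted within 7 calendar days of learning of the AE".

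**The concern.** A consented patient can undergo a study procedure with known procedural risks before any drug is given. The only sentence that says when AE reporting begins excludes that interval, while the definition a page earlier counts such complications as AEs. A site that follows 10.82 to the letter has grounds not to report a biopsy bleed or an infection at the clip site. A site that follows 10.81 or 10.62 would report it. Safety data on the procedure would then depend on which section the site happened to read.

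This matters most in Arm C, the only arm still open. There the clip marks the index node for objective 2.39a, so its placement serves the research and its safety belongs in the study record.

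The mismatch in expedited timelines is a smaller matter of the same kind: the glossary and the operative table do not give a site the same numbers.

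**Working it through.** No arithmetic decides this point; the check is to set the sections side by side.

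**1. Order of events.**
- Section 6.13: a signed consent form must exist before pre-registration is accepted.
- Section 17.1: the baseline core biopsy is collected after consent to the pre-registration phase, and an archival specimen is acceptable instead.
- Sections 4.1 and 4.2: the biopsy or archival specimen sits in the pre-registration column. Section 4.2 adds the clip.
- Section 6.27: treatment cannot precede registration.

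The sequence is therefore consent, then biopsy and clip where done, then registration, then first dose.

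**2. Is a complication an AE?** For a patient without archival tissue, the biopsy with clip is a protocol-mandated intervention. A complication meets the first Section 10.81 item quoted above. The second item shows that onset before treatment does not by itself disqualify it.

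**3. Is it inside the reporting period?** Section 10.82 joins two conditions, consent and start of treatment. At the time of the biopsy the first is met and the second is not, so the event falls before the period opens.

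**4. Does another section supply a start date?**
- Section 10.0: site investigators report SAEs to the sponsor whatever the attribution. No start is given.
- Section 10.41: the heading gives only an end point, 30 days after last administration.
- Section 10.62: Grade 2 events related to treatment or procedure, and Grade 3–4 events whatever the attribution. No start is given.
- Section 10.51: unanticipated problems related to taking part in the research. It is not tied to first dose.
- Sections 4.1 and 4.2 schedule an AE assessment within 14 days before registration, but the baseline list in Section 10.61 has no item for bleeding, wound infection or procedural pain.
- Section 13.6: for a patient removed before any treatment, only on-study material and a notification form are due.

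These sections create duties that could cover the event. None states a start that would displace 10.82.

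**5. Expedited timelines to the sponsor.**
- Section 10.0 definition: 24 hours, 5 days, 10 days. None is tied to a grade or event type.
- Section 10.41, Grade 3–5: 24 hours, then a complete report within 3 calendar days.
- Section 10.41, Grade 1–2 with hospitalization of at least 24 hours: 7 calendar days.

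The only shared value is 24 hours. The 5 and 10 days appear nowhere in 10.41; the 3 and 7 days are missing from the definition.

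**6. How many patients.** Sections 16.1112 and 16.132 plan 32 Arm C patients who start treatment, plus up to 4 replacements for those who refuse to start: 32 + 4 = 36. The share without archival tissue is not given, so the number needing a new biopsy lies between 0 and 36. Pre-registered patients who never register come on top of that, and their number is not stated. For anyone who never starts treatment, the 10.82 period, read literally, never opens.

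**The case against.** The strongest defence is that the quoted sentence sits in Section 10.8, the drug supplier's additional instructions. This is template text: 10.81 still carries an unfilled placeholder for the condition under study. The plan's own core duties in Sections 10.0, 10.41, 10.51 and 10.62 have no treatment-start condition, and Section 10.3 provides for attribution to a procedure. This stands in part. It shows that a reader who infers that nothing need be reported before first dose, or that such events would go unrecorded, goes further than the text. It does not remove the conflict. Section 10.82 covers reporting to the FDA and the IRB as well as the supplier, and it is the only place that gives a start.

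Four other inferences are tempting and not supported:
- *That every patient has a mandated biopsy.* The tissue is mandatory; a new biopsy is not, because archival tissue is accepted. Stage III must be confirmed histologically anyway (3.31), so a suitable specimen may already exist.
- *That the biopsy is the sole procedure before drug.* Research blood draws, swabs and an ECG also come before first dose, and in Arms A and B so do cardiac imaging and an eye examination.
- *That the length of the uncovered interval can be computed.* Adding the imaging look-back to the time allowed from registration to treatment measures imaging to dose. The documents do not fix the time from consent to dose.
- *That one SAE could be due at either 24 hours or 10 days.* The definition assigns 10 days to no event, and Section 10.41 binds Grade 3–5 SAEs to 24 hours plus 3 days. The one-business-day limit in Section 10.84 goes to the supplier, a different recipient, so it is not a competing deadline either.

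**Conclusion.** The point holds as a contradiction between sections. Section 10.82, read literally, excludes complications that Section 10.81 counts as AEs, for a biopsy or clip placement done after consent and before first dose. Other sections carry duties without a start date, so the plan is inconsistent and not silent.

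This rests on two readings: that the two conditions in 10.82 must both be met, as its wording says, and that a biopsy done because no archival tissue is available is protocol-mandated. The effect is confined to safety reporting; no pCR or RFS estimate changes. It should be corrected, because it concerns participant safety and the remedy is small.

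The expedited-reporting mismatch is real but secondary: a glossary entry that disagrees with the operative table. No section sets a 10-day deadline for any SAE.

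**What to change.** In Section 10.82, start the reporting period at pre-registration consent for SAEs and for AEs related to protocol-mandated procedures, and at first dose for all other AEs. Add one CRF instruction telling sites where to record a procedure-related event before first dose, including for patients who do not go on to treatment. The cost is the wording change, the instruction and a few more reports. Limiting the earlier start to SAEs and procedure-related AEs avoids collecting unrelated minor events during screening.

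As a secondary clean-up, replace the three time limits in the Section 10.0 definition of expedited reporting with the Section 10.41 timelines, or with a cross-reference to them. This is a wording change only.
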